9.5.3 Sample weighting

Since the relative weight of each region in the final sample will be different from its real relative weight in estimations, the extrapolation of the raw survey results to the overall target population would not be relevant without weighting. Thus, the survey results will be weighted to reflect the real proportion of the HCPs or vaccinees in participating regions. Both unweighted (i.e. raw data) and weighted results will be presented in the report.

²⁾ Please note that there is a high variation between vaccine centres in practice concerning the number of vaccinees per week (please see Table 4 of NaTHNaC Annual Return 2019)²³, and seasonality of vaccination for yellow fever. Data collection from March to May is the highest probable period of vaccination as per sales data.

³⁾ Based on similar design in UK

⁴⁾ NaTHNaC Annual reports figures adjusted to include Scotland

A weight variable will be applied to each statistical unit during the results calculation in order to correct any over- or under-sampling that may have occurred for a region or a target population. This weight variable will indicate how many unit(s) of the population of interest an observation will count in a statistical procedure. Its value will change per region. The weights will be normalised to obtain a sum equal to the sample size.

The number of YFVCs as reported by NaTHNaC¹⁷ and HPS¹⁸ in each region and the median number of qualified HCPs per YFVC will be used to determine the universe, to weight back HCPs' samples. For vaccinees, an approximation of the vaccinees' universe will be obtained from the vaccine sales data of each region provided by the MAH.

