9.2.4.1 HCPs selection

It is expected that nurses will represent the majority of HCPs in the YFVCs. Other HCPs to be included in the study will be general practitioners, and a minority will be pharmacists.¹⁶

The initial identification of participating HCPs will be based on the list of all YFVC practices as reported by the NaTHNaC¹⁷ in each region and HPS¹⁸. The lists of YFVCs will be reconciliated

with OneKey lists (OneKey, IQVIA) in order to retrieve contact details for HCPs working in each YFVC. OneKey is an IQVIA managed database with information of HCPs in each of the relevant specialities in the targeted country. OneKey databases are constructed and updated through manual and automated means from various sources, including publicly available sources. Information collected includes HCP personal information (e.g. age, gender, contact details) and professional information (e.g. year of graduation, specialties, practicing status). These lists are widely used for the recruitment of HCPs in clinical trials, observational studies and surveys.21, ²²

Since the study objective is to determine the extent of HCPs' awareness and knowledge of the safety information in the aRMMs, only HCPs who have provided consultation for yellow fever vaccine administration and/or administered the yellow fever vaccine in the past 12 months will be selected. As this information is not available in the lists of HCPs, the survey will be preceded by a set of questions to check the eligibility of HCPs. Among these, it will be asked if the HCP has provided consultation to yellow fever vaccinees and/or administered the yellow fever vaccine in the past 12 months. If the answer is "no", the survey will not open to that HCP.

According to the Annual Return 2020¹³ report, the number of HCPs administering yellow fever vaccines varied for each YFVC and around 89% of YFVCs had 1 to 3 HCPs administering yellow fever vaccines. Therefore, to limit selection bias, we will recruit a maximum of 3 HCPs per centre. However, in case the target sample size is not achieved, this cap may be lifted to a maximum of 5 HCPs per centre.

HCPs recruitment and survey will be conducted by the following process:

- HCPs will be invited to participate in the survey by email and/or phone. An email
 invitation will include a web link directing to the questionnaire. In the invitation, the
 survey background and objectives, the contact information for questions, and the proposed

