9.5.2 Sample size feasibility

In 2019, there were 2,821 YFVC (5,474 HCPs) in England, Wales, and Northern Ireland.²³ However, the number of YFVCs and the frequency of travel, especially to endemic countries, have been significantly affected by the COVID-19 pandemic. There were 2,295 YFVC (3,763 HCPs) which remained designated in 2020,¹³ suggesting a 19% decrease compared to 2019. The average number of yellow fever vaccine doses given per centre decreased from 47 (median: 22) in 2019 to 13 (median: 5) in 2020, which corresponds to a decrease of 72%. Sales of the yellow fever vaccine went from around doses in 2019 in the UK, to around doses in 2020, representing a 71% fall.

The dynamics of vaccine centres, vaccinees and number of doses administered are still not stabilised. Therefore, a sample size feasibility assessment will be done before the start of fieldwork to predict the likelihood of achieving the desired sample size and to eventually adjust the sample size.

For this assessment, the updated number of YFVCs, the number of vaccinees and the sales of the vaccine will be estimated. The YFVC will be matched with the OneKey database and HCPs will then be identified through OneKey as detailed in Section 9.2.4. This will provide an actualised number of identified HCPs.

The number of vaccinees will be estimated using the most recent sales data of STAMARIL® received by the MAH at the time of the feasibility assessment.

For HCP survey, the number of HCPs that will be included in the survey will be estimated based on a response rate of 5-10%. Therefore, for a sample size of 200 HCPs, between 2000 to 4000 HCPs will have to be contacted. Using the results of this assessment of the actual numbers of HCPs at the time of the survey will allow us to adjust the target sample size.

For vaccinee sample size assessment, the number of vaccinees who will complete the web/paper questionnaires will be estimated using a process as presented in Table 3. Participation rates may vary around the figures presented in this table. However, with a yearly population of vaccinees of around (as presented for 2019) it is possible to recruit around 174 vaccinees, while only 37 could be recruited with a yearly population of (as in 2020). Using the most recent numbers of vaccinees at the time of the survey will allow to adjust the target sample size.

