9.7 DATA ANALYSIS

General statistical considerations

The statistical analysis will be conducted using the SAS® software V9.4 (SAS Institute North Carolina, USA), or R version 3.6 or higher on WindowsTM. All the analyses will be descriptive. Continuous variables will be described by their number (of valid cases, of missing values), mean, standard deviation, and median, Q1, Q3, minimum and maximum. Categorical variables will be described as the total number and relative percentage per category.

In case of multiple-choice questions, the frequency of each option provided by the HCPs/vaccinees will be reported as the total number and relative percentage per category. Different combinations of the answers provided (if any) will not be considered.

Wilson CIs of 95% will be evaluated on the overall result.

The participation rate will be analysed overall and per region for HCPs and vaccinees separately.

The proportion of correct and desirable answers to the selected questions asked in the questionnaire will be separately expressed for HCPs and vaccinees (or their parents/guardians if vaccinees are younger than 18 years old) who provide answers to those questions (the missing data will not be counted as a denominator in proportions). Success indicators by objectives will be presented separately for HCPs and vaccinees.

In the first step, calculations will be performed overall and per region on raw data. In the second step, only overall results will be weighted according to the proportion of HCPs and vaccinees in each region in order to accurately reflect the population that the survey seeks to measure. Estimation of HCPs' universe will be determined using the number of YFVCs in each region and median of qualified HCPs in YFVCs obtained from the official websites of NaTHNaC¹⁷ and HPS¹⁸. For vaccinees, approximation of vaccinees' universe will be obtained from the vaccine sales data of each region provided by the MAH.

The statistical results will be presented in the same report, as overall and per region for both of the questionnaires.

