9.9.2 Limitations

1. Bias

Selection bias

a. HCPs survey

The potential for selection bias of HCPs participating in a survey is an inherent limitation to any study based on volunteer participation. For instance, it is possible that HCPs willing to participate in the study will have the highest awareness of risks associated with use of STAMARIL®. In order to quantify any selection bias, the distribution of each stratification criterion of HCPs (region, HCP profession, and other demographic information collected) will be compared between participants and non-participants.

Non-response bias may also be introduced into the study if targeted HCPs have activated filters in their mailbox that block spam and unsolicited emails. If a very strict degree of message filtering is set, they may not even see the invitation to participate in the survey. Having multiple email addresses could also be a critical situation. If the one used is not the primary address or if the HCPs do not check their emails frequently, they will not receive the invitation during the recruitment period. Some HCPs who are sent a letter may not receive it. This is one of the reasons why the HCPs will also be contacted by phone.

b. Vaccinee survey

For the vaccinees' recruitment by HCPs (who participate or do not participate in the HCPs' survey [in case the target vaccinee sample size is not achieved]), who are aware of the UK (STAMARIL®) yellow fever pre-vaccination checklist and provide the STAMARIL® PIL to the vacinees are more likely to participate in recruiting vaccinees for the patient survey.

HCPs will consecutively solicit vaccinees for participating in the survey. The recruitment of vaccinees will occur in the defined study period and until the limit of ten vaccinees per YFVC is reached. Although consecutive recruitment should minimise selection bias, HCP compliance to this approach cannot be verified. The characteristics of the vaccinees who will not fulfil eligibility criteria cannot be captured, so it is not possible to know the extent of the selection bias.

Information bias

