Recall bias may lead to an underestimation of the HCP recalling having received aRMMs. To mitigate the risk of recall bias for HCPs, they will be recruited in the survey if they have provided consultation and/or administered yellow fever vaccines in the past 12 months. Also, to mitigate the risk of recall bias for vaccinees or their parents/guardians if vaccinees are younger than 18 years old, they will be immediately provided with material for the web/paper survey after receiving the vaccine/consultation.

Moreover, web surveys may promote social desirability bias, which refers to the tendency of HCP to give socially desirable/expected responses instead of choosing those reflecting their current knowledge or behaviour, e.g. physicians can copy-paste information gathered online instead of giving their own opinions. Social desirability can affect the validity of survey research findings, but the use of prepopulated items in the questionnaire could/tends to reduce this bias. The access to the web questionnaire interface will be strictly limited to the invited participants, with the possibility to participate only once, and a traceability system. Thus, stakeholder bias (multiple answers of people who have a personal interest in survey results and/or who incite peers to fulfil the survey in order to influence the results) or unverified respondents (when it is not possible to verify who responds) are not applicable.

2. Generalisation of the survey results to the overall target population

In such surveys, the generalisation and external validity of the results is restricted to HCPs/vaccinees who can be reached and are willing (and able) to answer a questionnaire online or paper questionnaire (only for vaccinees). These HCPs/vaccinees may not be fully representative of the whole target population.²⁷

Although the raw survey results cannot be generalised to the overall target population, a sample adjustment will be implemented to allow the generalisation of the results. For more transparency and accuracy, both unweighted (i.e. raw data) and weighted results by region will be presented in the report.

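### The HCP weights are built from centres and the median HCPs per centre, so they follow centre counts rather than HCP counts, and Section 9.9.2 credits regional weighting with more than it can do

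*Protocol*

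**What the plan says.** Section 9.5.3 sets the purpose of the weights: "the survey results will be weighted to reflect the real proportion of the HCPs or vaccinees in participating regions". The weight depends on region alone ("Its value will change per region"), and the weights are scaled so that their sum equals the sample size.

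For HCPs, the regional population comes from the number of YFVCs per region, and "the median number of qualified HCPs per YFVC will be used to determine the universe". Section 9.7 repeats this: "Estimation of HCPs' universe will be determined using the number of YFVCs in each region and median of qualified HCPs in YFVCs". The Abstract carries the same rule under data analysis. The multiplication of centres by median is not written out, but no other use of a per-centre median would give a population size. The text does not say whether there is one national median or one per region, and it gives no value.

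Section 9.5.2 quotes HCP totals as well as centre totals: "There were 2,295 YFVC (3,763 HCPs) which remained designated in 2020" (England, Wales and Northern Ireland). Table 3 gives UK totals of both.

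On what the weighting achieves, Section 9.9.2 says that raw results cannot be generalised but that "a sample adjustment will be implemented to allow the generalisation of the results".

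**The concern.** A regional total of HCPs is the number of centres times the mean number per centre, or a direct count. The median is a different quantity. HCPs per centre is a small whole number with some larger centres (Section 9.2.4.1: "around 89% of YFVCs had 1 to 3 HCPs administering yellow fever vaccines"), so mean and median need not agree.

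The rule therefore does not deliver the HCP shares that Section 9.5.3 asks for. If the mean number of HCPs per centre differs between regions, regions with fewer HCPs per centre get too much weight and the others too little. The weighted overall percentages are compared with the 80% success threshold, so a shift matters if a result lies close to it.

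The second issue is the sentence on generalisation. Weights that vary only by region can correct only regional over- or under-representation. They cannot correct for who chooses to answer within a region, at an assumed HCP response rate of 5-10% (Section 9.5.2).

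**Working it through.** **Inputs**
- England/Wales/Northern Ireland (E/W/NI), Section 9.5.2: 2,821 centres and 5,474 HCPs in 2019; 2,295 centres and 3,763 HCPs in 2020.
- UK, Table 3 rows B and C: 2,989 centres and 5,668 HCPs (first column, taken as 2019); 2,418 centres and 3,905 HCPs (2020).
- Scotland, Section 9.2: 168 centres (January 2021) and 123 centres (January 2022).
- Median HCPs per centre: not given.

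**Step 1. Reproduce the protocol's totals**
- Centres: 2,821 + 168 = 2,989 and 2,295 + 123 = 2,418. Both match Table 3.
- Mean HCPs per centre in E/W/NI: 5,474/2,821 = 1.94 (2019); 3,763/2,295 = 1.64 (2020).
- UK centres times that mean: 2,989 × 1.940 = 5,800 against 5,668 (+2.3%); 2,418 × 1.640 = 3,965 against 3,905 (+1.5%). Centres times the mean roughly recovers the stated HCP totals.

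**Step 2. What the planned rule gives after normalisation**

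With c_r centres in region r and a common median m, the share of region r is m·c_r / (m·Σc) = c_r / Σc. The median drops out, and the weights are proportional to centres.

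**Step 3. Scotland, by subtraction**
- 2020: 3,905 − 3,763 = 142 HCPs in 123 centres, or 1.15 per centre.
- 2019: 5,668 − 5,474 = 194 HCPs in 168 centres, or 1.15 per centre.

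| | Share of centres (planned weight) | Share of HCPs (stated aim) | Ratio |
|---|---|---|---|
| 2020 | 123/2,418 = 5.1% | 142/3,905 = 3.6% | 1.40 |
| 2019 | 168/2,989 = 5.6% | 194/5,668 = 3.4% | 1.64 |

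**Step 4. Effect on an overall percentage**

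Shift = (planned share − HCP share) × gap between Scotland and the rest. The gap is an assumption.
- 2020: (5.09% − 3.64%) × 10 points = 0.15; × 20 points = 0.29.
- 2019: (5.62% − 3.42%) × 10 points = 0.22; × 20 points = 0.44.

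For comparison, the 95% half-width with 200 HCPs at 80% is 1.96 × √(0.8 × 0.2/200) = 5.5 points (normal approximation).

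**Step 5. How far this rests on the Scottish figure**

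The Scottish ratio is 1.15 in both years while the E/W/NI ratio fell from 1.94 to 1.64. A footnote to Table 3 says that the figures were adjusted to include Scotland, so the 142 and 194 may reflect an assumed multiplier rather than counts. If Scotland really had the E/W/NI mean, its HCP share would equal its centre share and the error for Scotland would vanish.

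**Step 6. The generalisation sentence**

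In Section 9.9.2, the paragraph just before it restricts external validity to those who can be reached and are willing to answer. The selection-bias text in the same section allows that participating HCPs may be the most aware of the risks. It plans that "the distribution of each stratification criterion of HCPs (region, HCP profession, and other demographic information collected) will be compared between participants and non-participants", but no adjustment follows from that comparison. A weight constant within region leaves this self-selection unchanged.

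**The case against.** The strongest reply is that it hardly matters. The analyses are descriptive, raw and weighted overall results are both reported, and the shift is a fraction of a point against a half-width above 5 points. That stands, and it limits the weight of this point. It does not make the rule right, since the weighted figure is offered as the one that reflects the population.

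It is also fair that the better input is not fully in hand. The protocol shows one pooled E/W/NI count, not four regional ones. Table 3 counts HCPs involved in vaccinations, whereas the weights concern qualified HCPs. Contacts identified through OneKey are not screened for activity in the past 12 months. These limits apply to the replacement, but a per-centre median does not overcome them.

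Four stronger readings are tempting, and the protocol does not support them.
- **The population size is badly wrong.** A median of 1 would give 2,418 HCPs against 3,905 (−38%), and a median of 2 would give 4,836 (+24%). Normalisation removes any common factor, so these errors affect no result.
- **A region's weight could jump by a factor of two**, with a median of 2 in one region and 1 in another. This needs separate regional medians, which the text does not state. Further, if every centre has at least one HCP and the 11% outside the 1-to-3 range have four or more, a 2020 E/W/NI median of 2 needs a mean of at least 0.50 × 1 + 0.39 × 2 + 0.11 × 4 = 1.72, above the actual 1.64.
- **The weights should also be raked to profession.** The protocol gives no population margins for profession, and its stated aim is regional correction. This is a matter of preference.
- **The report will claim unqualified generalisability.** Section 9.9.2 already contains the caveats; one clause runs ahead of them.

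**Conclusion.** The point holds in a limited form. The rule in the Abstract, Section 9.5.3 and Section 9.7 does not estimate regional HCP totals. With one median, or equal medians, it weights by centres although Section 9.5.3 asks for weighting by HCPs. On the 2020 figures Scotland would get about 5.1% instead of about 3.6%, conditional on a Scottish HCP count obtained by subtraction from adjusted totals. The consequence for overall results is about 0.3 points for an assumed 20-point gap (0.4 on the 2019 figures), so it could change a conclusion only very near the 80% threshold. Any distortion among England, Wales and Northern Ireland is unknown, because the protocol does not separate them.

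The clause in Section 9.9.2 that the adjustment allows generalisation is too strong for weights that vary only by region, and it sits uneasily with the limits stated around it.

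**What to change.** 1. In the Abstract, Section 9.5.3 and Section 9.7, replace the median with the number of HCPs in each region. Take it from the annual return and Public Health Scotland counts, or from the OneKey-matched count already planned in Section 9.5.2. If only per-centre data are available, use centres times the regional mean. State which HCPs are counted and how that group differs from qualified HCPs.
2. In Section 9.9.2, replace the generalisation clause with a statement that the weights correct regional imbalance only and that the self-selection described in the same section remains.

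The cost is wording in four places and obtaining the regional split of HCP numbers. If the median was to be calculated from per-centre counts, the same counts give the mean and the total. If only a published median was to be used, the regional totals must be requested. Sample size, questionnaires and fieldwork are unaffected.

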9.6 DATA MANAGEMENT

9.6.1 Data collection schedule

The data collection period will last about 12 weeks (fieldwork) or longer if needed (up to 24 weeks).

9.6.2 Data collected

Data related to the variables listed in Section 9.3.1 and 9.3.2 will be collected from the HCP and vaccinee questionnaires, respectively.

9.6.3 Survey questionnaire

The HCP and vaccinee questionnaires are separate stand-alone documents included in Annex 1.

9.6.4 Participant tracking log

A fully anonymous tracking log will be used to collect HCP information.

9.7 DATA ANALYSIS

General statistical considerations

The statistical analysis will be conducted using the SAS® software V9.4 (SAS Institute North Carolina, USA), or R version 3.6 or higher on WindowsTM. All the analyses will be descriptive. Continuous variables will be described by their number (of valid cases, of missing values), mean, standard deviation, and median, Q1, Q3, minimum and maximum. Categorical variables will be described as the total number and relative percentage per category.

In case of multiple-choice questions, the frequency of each option provided by the HCPs/vaccinees will be reported as the total number and relative percentage per category. Different combinations of the answers provided (if any) will not be considered.

Wilson CIs of 95% will be evaluated on the overall result.

The participation rate will be analysed overall and per region for HCPs and vaccinees separately.

The proportion of correct and desirable answers to the selected questions asked in the questionnaire will be separately expressed for HCPs and vaccinees (or their parents/guardians if vaccinees are younger than 18 years old) who provide answers to those questions (the missing data will not be counted as a denominator in proportions). Success indicators by objectives will be presented separately for HCPs and vaccinees.

In the first step, calculations will be performed overall and per region on raw data. In the second step, only overall results will be weighted according to the proportion of HCPs and vaccinees in each region in order to accurately reflect the population that the survey seeks to measure. Estimation of HCPs' universe will be determined using the number of YFVCs in each region and median of qualified HCPs in YFVCs obtained from the official websites of NaTHNaC¹⁷ and HPS¹⁸. For vaccinees, approximation of vaccinees' universe will be obtained from the vaccine sales data of each region provided by the MAH.

The statistical results will be presented in the same report, as overall and per region for both of the questionnaires.

